Sample size calculations focused on the change from baseline to 24 weeks in muscle power and were conducted for a factorial analysis (at-the-margins analysis), i.e. a) the comparison between all participants allocated to KHCO₃ vs. all those not allocated to KHCO₃ and b) the comparison between all participants allocated to whey protein vs. all those not allocated to whey protein. We will test each of these two primary hypotheses with a two-sided test and significance level 0.05. There will be no adjustment for multiplicity because, under the assumption of no interaction (the effect of whey protein is the same whether the patient is allocated to KHCO₃ or not, and similarly for KHCO₃), that is inherent to a factorial analysis, our trial answers two distinct research questions, and statistical simulation support that no adjustment is needed in this scenario. All secondary and exploratory analyses are considered as supporting the primary analysis, with two-sided tests and significance levels of 0.05.

Table 1 shows the hypothesized mean changes in muscle power in each of the 4 randomization groups. For the comparison of KHCO₃ vs. no KHCO₃, the hypothesized mean change is 10% (with) and 4% (without). We assumed a common standard deviation (SD) of change in power to be approximately 12%, based on the subset of men and women over age 65 in a previous study of the effect of HCO₃⁻(1). Sample sizes of 60 and 60 in KHCO₃ vs. no KHCO₃ yield 80% power to detect a between-group difference of at least 6%. This effect size was observed in the subset of older men and women in the previously referenced study (1). For the comparison of whey protein vs. no whey protein, the hypothesized mean change in muscle power from baseline to follow-up is 11% (with) and 3% (without). We assumed a common SD of change in power to be 15%. Sample sizes of 60 and 60 in whey protein vs. no whey protein yield 80% power to detect a between-group difference of at least 8%. This effect size was observed when subjects in the previous study (1) were divided into high and low protein groups based on their self-selected diets.

Table 1: Hypothesized change in leg power by intervention

		KHCO ₃		
		yes	No	Overall
Whey protein	Yes	14% N=30	8% N=30	N=60
	No	6% N=30	0% N=30	N=60
	Overall	N=60	N=60	

d. Framework

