For all objectives, we use a superiority framework and a factorial analysis (at-the-margins analysis), i.e., testing the superiority of whey protein against no whey protein and of KHCO₃ against no KHCO₃.

e. Statistical interim analyses and stopping guidance

No formal statistical interim analysis was planned. The Data and Safety Monitoring Board (DSMB) periodically evaluated enrollment data, AE, and SAE by randomization group.

f. Timing of final analysis

Final analysis will take place after all data for the primary and secondary outcomes have been collected, data cleaning is complete, and after this SAP is finalized and posted on clinicaltrials.gov.

g. Timing of outcome assessments

Outcomes are measured at baseline, 12 weeks, and 24 weeks after randomization.

5. Statistical Principles

a. Confidence intervals and P values

All statistical tests will be 2-sided. We will use $p \leq 0.05$ to indicate statistical significance for the primary outcome for each of the two primary comparisons of interest in a factorial analysis (at-the-margins analysis): a) the comparison between all participants allocated to KHCO₃ vs. all those not allocated to KHCO₃ and b) the comparison between all participants allocated to whey protein vs. all those not allocated to whey protein. Under the assumption of no interaction that is inherent to a factorial analysis, the primary analyses test two independent hypotheses, and no multiplicity adjustment is needed in this scenario. All secondary and exploratory analyses are considered as supporting the primary analyses, with two-sided tests and significance levels of 0.05.

b. Adherence and protocol deviations

Adherence to study pills was assessed by capsule counts and by capsule diaries. Adherence to the protein packets was assessed by packet counts and diaries. Objective measures of adherence are urinary net acid excretion (NAE) and UNi.

Major protocol deviations for the trial include:

1. Participant found ineligible after randomization
2. No informed consent signed
3. Participant didn't receive the randomly allocated intervention
4. Withdrawal of consent for future data collection, and/or ongoing use of previously collected study data

c. Analysis populations

The full analysis set will include all randomized subjects. Following the intention-to-treat (ITT) principle, subjects will be analyzed according to the group they were assigned to at randomization regardless of treatments received.

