 16. other condition or abnormality in screening labs, at discretion of the study physician

b. Recruitment

We will use a CONSORT flow diagram to summarize the number of participants who:

- were assessed for eligibility at screening
- were eligible at screening
- were invited to participate
- provided consent
- were randomized
- withdrew prior to receiving treatment

- included in the primary analyses

The flow diagram will also show the numbers who were eligible but not randomized, who did not receive the randomized allocation, who discontinued the intervention, and we will describe the reasons.

c. Withdrawal/follow-up

The level of withdrawal will be tabulated and classified as “consent to continue follow-up and data collection”, “consent to continue data collection only”, “complete – no further follow-up or data collection”. The numbers (with reasons) of losses to follow-up (drop-outs and withdrawals) over the course of the trial will be summarized by randomization group.

d. Baseline patient characteristics

Participants will be described at the time of randomization with respect to age, sex, race and ethnicity, weight, BMI, blood pressure, physical activity assessment, DXA lean tissue mass, D₃-creatine dilution, double leg press power testing, knee extensor strength, handgrip strength, modified SPPB, total energy intake, dietary protein intake, and fruit and vegetable intake. All characteristics will be first tabulated overall and separately for whey protein vs. no whey protein and KHCO₃ vs. no KHCO₃. We will then tabulate the characteristics in each of the four cells of the 2x2 design. Categorical data will be summarized by numbers and percentages, and continuous data by mean, SD (or median, Q1-Q3 if data are skewed). No tests of statistical significance will be performed; any imbalance of clinical importance will be noted.

7. Analysis

a. Outcome definitions

Primary outcome: Keiser double leg press power at 70% at 24 weeks. Following one-repetition maximum measurement (1RM), the participant performs 5 presses at 70% of their 1RM as fast as possible through their full range of motion. The highest power output is determined to be the peak power.

Secondary outcomes:

- Double leg press peak power at 70% of 1RM at 12 weeks
- Double leg press peak power at 40% of 1RM at 12 and at 24 weeks
- Knee extension peak torque at 60°/sec at 12 and 24 weeks
- Maximum handgrip strength at 24 weeks
- Appendicular lean mass/ht² by DXA at 24 weeks

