- Health ABC-PPB score at 24 weeks
- 24hr urinary nitrogen excretion

Exploratory:

- muscle mass as measured by D₃-creatine dilution at 24 weeks

b. Analysis methods

Summary statistics. For each outcome, we first will report summary statistics at each timepoint for whey protein vs. no whey protein and for KHCO₃ vs. no KHCO₃. We will then report summary statistics in each of the four cells of the 2x2 design. We also will create box plots that display the distribution of the data at each time point for each comparison.

Primary Outcome. Primary analyses of the primary outcome will be performed on the ITT sample based on an ANCOVA comparing 24-week leg power with fixed effects for intervention groups and further adjustment for leg power at baseline, age and sex. Moreover, the effect of each intervention will be adjusted for the other intervention. Type III sum-of-squares will be used to test significance of each intervention. Least squares mean difference between intervention groups, and 95% confidence intervals, based on the fitted linear models will be reported.

Table 2: Presentation of the results of the primary analyses

	Whey protein	No whey protein	KHCO ₃	no KHCO ₃
Leg power, mean (SD)	xx.x (xx.x)	xx.x (xx.x)	xx.x (xx.x)	xx.x (xx.x)
LS mean difference (95% CI)*		-xx.xx (-xx.x to -xx.x)		-xx.xx (-xx.x to -xx.x)
p value		xxx		Xxx

*adjusted for sex, age, leg power at baseline, and factorial design

Secondary analyses and secondary outcomes.

- We also will conduct factorial analyses of all secondary outcomes by using similar analytic approach to the primary outcome.
- In addition of ANCOVA analyses, we will fit longitudinal model based on all repeated measurements of the outcome, i.e., a linear model with 12-week and 24-week measurements as outcome observations and fixed effects for the intervention group, time treated as categorical, intervention group by time interaction, baseline measure, baseline measure by time interaction, and sex. The corresponding treatment effect measure is the between-group difference in the slopes of the mean responses. Restricted maximum likelihood estimation will be used with the Newton–Raphson algorithm. An unstructured covariance matrix will be used to model the variance-covariance matrix for random intercept and random slope. In the case of nonconvergence with UN, a toeplitz covariance matrix will be used. In the case of nonconvergence with TOEP, an autoregressive covariance matrix [AR (1)] will be used.

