Difference in estimated least square mean slopes, the corresponding 95% CI, and p-value will be reported. We will use the p value from the type III F-test of the fixed effect parameter for the intervention group by time interaction. Denominator degrees of freedom will be estimated using the Kenward-Roger approximation with an unstructured covariance matrix and the between-within method otherwise.

- We also will present results for outcome measures at follow-up within each of the four factorial groups in the 2×2 design. We will test for interaction by extending the multivariable linear models described above by simply adding the appropriate interaction terms. However, we anticipate insufficient precision on the interaction estimates to rule out interaction.
- We will repeat analyses in the mITT and per protocol samples.

c. Subgroup Analyses

We will perform subgroup analyses by sex, NAE (<15 mmol/day vs. ≥ 15 mmol/day), protein intake based on average 3-day food recall (≤ 0.8 gm/kg/day vs. > 0.8 gm/kg/day), no sarcopenia vs. sarcopenia (defined as maximum grip strength <35.5 kg (men) and <20 kg (women) in either hand and/or gait speed <0.8 m/sec.

d. Missing data

Descriptive tables of baseline characteristics stratified by arm will include the frequency and percentage of missing values. In attrition analyses, we will then compare these variables between subjects who drop out and subjects with complete outcome data. The number of missing primary outcome data points at each time point, by intervention arm, will be reported in the CONSORT participant flow diagram.

For the primary analyses, we will analyze all available follow-up outcome data using restricted maximum likelihood estimation, under the assumption that data are missing at random.

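### The longitudinal model reports group-by-time as the treatment effect, but with only weeks 12 and 24 as outcomes that term tests whether the effect changed after week 12, not whether there is one

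*SAP*

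**What the plan says.** The primary analysis in SAP section 7.b is an ANCOVA of 24-week leg power, adjusted for baseline power, age, sex and the other intervention. The secondary outcomes get a similar analysis.

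A further model is then specified: "In addition of ANCOVA analyses, we will fit longitudinal model based on all repeated measurements of the outcome". It is "a linear model with 12-week and 24-week measurements as outcome observations", with fixed effects for group, categorical time, group by time, baseline, baseline by time, and sex. Its estimand is stated: "The corresponding treatment effect measure is the between-group difference in the slopes of the mean responses". The reported quantities are the difference in least-squares mean slopes, its confidence interval and a p-value. On the p-value: "We will use the p value from the type III F-test of the fixed effect parameter for the intervention group by time interaction".

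On the covariance: "An unstructured covariance matrix will be used to model the variance-covariance matrix for random intercept and random slope". Toeplitz and then AR(1) are the fallbacks if the model does not converge.

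The model can apply only to outcomes measured at both follow-up visits. In section 7.a these are leg press power at 70% of 1RM (the primary measure), knee extension torque, and "Double leg press peak power at 40% of 1RM at 12 and at 24 weeks".

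Section 7.d separately says that the primary analyses use all available follow-up outcome data by REML under missing at random.

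**The concern.** A difference in slopes measures the effect since randomization when baseline is one of the outcome rows. Here it is not. Baseline has been moved to the right-hand side, so the arms are already equated at baseline and the treatment effect sits in the level at each visit. The group-by-time term carries only the change in that effect between weeks 12 and 24. The SAP names no week-24 contrast, averaged group effect or joint test for this model.

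Two misleading results can follow. A benefit reached by week 12 and maintained would usually give a null p-value for what the plan calls the treatment effect, printed beside a positive week-24 ANCOVA. A benefit that is real at both visits but smaller at week 24 would give a negative treatment effect. Section 5.a says of such analyses: "All secondary and exploratory analyses are considered as supporting the primary analyses". This one could be read as contradicting the primary result when it does not address the same question. The analyses are also to be repeated in the mITT and per-protocol samples.

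**Working it through.** **What the interaction is.** Let d12 and d24 be the adjusted effects of one factor at the two visits. With a two-level categorical time, the group-by-time coefficient is d24 − d12. If d12 = d24 it is zero, however large the effect.

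**Inputs from SAP section 4.c.** KHCO3: difference 6%, SD of change 12%. Whey: difference 8%, SD 15%. Both comparisons are 60 versus 60, two-sided 0.05, with stated power 80%.

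**Assumptions not in the documents.** The same SD applies at week 12; the correlation r between the week-12 and week-24 values is 0.5, 0.7 or 0.9; and the share of the week-24 effect already present at week 12 is varied.

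**The plan's own figure (noncentral t, 118 df).**
- KHCO3: SE = 12·√(2/60) = 2.191; 6/2.191 = 2.739; power 77.5%.
- Whey: SE = 15·√(2/60) = 2.739; 8/2.739 = 2.921; power 82.6%.

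These lie within 3 points of the stated 80% and serve as the benchmark for the week-24 contrast.

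**Group-by-time test.** SE = SD·√(2(1−r))·√(2/60).
- KHCO3: 2.191, 1.697 and 0.980 at r = 0.5, 0.7 and 0.9.
- Whey: 2.739, 2.121 and 1.225.

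Example: KHCO3 with half the effect by week 12 and r = 0.7 gives 3/1.697 = 1.768, hence 42% power.

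| Share of effect present by week 12 | KHCO3 power, r = 0.5 / 0.7 / 0.9 | Whey power, r = 0.5 / 0.7 / 0.9 |
|---|---|---|
| All, maintained | 5% / 5% / 5% | 5% / 5% / 5% |
| Three quarters | 10% / 14% / 33% | 11% / 15% / 37% |
| Half | 27% / 42% / 86% | 30% / 46% / 90% |
| Week-24 contrast, any share | 78% | 83% |

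The whey entry of 30% is 30.5% before rounding.

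**Simulation** of the 2×2 design (30 per cell, both factors active, 8,000 runs per setting), maintained benefit: group-by-time rejected in 4.7% to 5.4% of trials. The week-24 contrast was significant in 77% to 78% (KHCO3) and 82% to 83% (whey). A significant week-24 contrast beside a non-significant group-by-time test occurred in about 74% to 75% (KHCO3) and 78% to 79% (whey).

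**Covariance.** An unstructured random intercept and slope has 3 parameters, and the residual adds a fourth. Two observations per person supply 3 covariance elements. Code time as 0 and 1, and take SD 12 and r = 0.7, so both variances are 144 and the covariance is 0.7 × 144 = 100.8. Three different parameter sets reproduce this matrix:

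| Residual variance | Intercept variance | Slope variance | Intercept–slope covariance | Week-12 variance | Covariance of visits |
|---|---|---|---|---|---|
| 5 | 139 | 76.4 | −38.2 | 139 + 5 = 144 | 139 − 38.2 = 100.8 |
| 20 | 124 | 46.4 | −23.2 | 124 + 20 = 144 | 124 − 23.2 = 100.8 |
| 40 | 104 | 6.4 | −3.2 | 104 + 40 = 144 | 104 − 3.2 = 100.8 |

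In each row twice the covariance cancels the slope variance, so the week-24 variance is also 144. All three sets are positive definite, and the likelihood cannot choose between them. The fixed-effect contrasts remain estimable.

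**Section 7.d against 7.b.** The primary ANCOVA has one row per person. Whether fitted by REML or least squares, it uses only participants with a week-24 value. A week-12 value from someone missing at week 24 does not enter, so the description in 7.d does not fit the model in 7.b.

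**The case against.** The strongest reply is that little depends on this model. It is additional to the ANCOVAs, which already test every affected outcome at each visit, so no primary estimate or p-value changes. That is right, and it limits the severity.

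Second, the 5% is simply alpha, because a fully maintained effect is the null hypothesis of the interaction, and the 74% to 79% discordance follows largely from that assumption. This also stands. These figures describe one scenario, and with a still-growing effect and a high correlation the test can have 86% to 90% power. The test is misdirected rather than always uninformative. The early-effect scenario is nevertheless plausible on the plan's own sources: section 4.c takes both planning differences from the earlier bicarbonate trial, which the protocol's Study Rationale describes as 12 weeks long.

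Third, the results would be labelled as a difference in mean slopes, which tells a careful reader what is shown. True, but the same section calls that difference the treatment effect measure.

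Fourth, the SAP has covariance fallbacks. They apply only on nonconvergence, and for a 2×2 matrix Toeplitz and AR(1) are the same structure.

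Fifth, the 7.d sentence may only mean an available-case analysis, which can be valid under missing at random given the covariates. The wide-format multiple imputation is also meant to preserve within-person correlation. Both are fair, so 7.d is a wording conflict and no bias is claimed.

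**Conclusion.** The concern holds. As written, the longitudinal model's declared treatment effect and p-value measure the change in effect from week 12 to week 24. If the benefit is complete by week 12 and held, the test has 5% power at any correlation, where the week-24 contrast has 78% (KHCO3) or 83% (whey). Partial early benefit gives intermediate values that depend strongly on r. The identity d24 − d12 needs no assumptions. The power figures rest on equal SDs at the two visits, the assumed r and the assumed week-12 share.

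The random-effects structure is not identifiable from two visits, though this does not prevent estimation of the contrasts. The scope is leg press power at 70% and 40% of 1RM and knee torque, in a supplementary model. The primary ANCOVA is not invalidated. This should be fixed before the analysis is run.

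**What to change.** In section 7.b:
- Fit weeks 12 and 24 with an unstructured residual covariance and no random effects.
- Include each intervention factor and its interaction with time, baseline, baseline by time, and sex. Age is optional, for consistency with the primary model.
- For each factor, report and test the adjusted difference at week 24 and at week 12, with confidence intervals and Kenward-Roger degrees of freedom.
- Keep group-by-time if wanted, labelled as a test of change in effect between weeks 12 and 24.

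In section 7.d:
- State that the primary ANCOVA uses participants with a week-24 value, and drop the REML description of it.
- Name the week-24 contrast from the corrected model as a supporting analysis under missing at random, beside the multiple imputation.
- Say outright that the week-12 outcome is in the imputation model.

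The cost is SAP wording and a few lines of code, with the same data and software. The primary estimator does not change. The one drawback is two visit contrasts per factor instead of a single p-value.

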9. significant immune disorder
10. current unstable heart disease
11. Crohn's disease
12. active malignancy or cancer therapy in the last year
13. alcohol use exceeding 2 drinks/day
14. current peptic ulcers or esophageal stricture
15. milk protein allergy
16. other condition or abnormality in screening labs, at discretion of the study physician ([name])

Withdrawal of subjects:

Participants are free to stop participation at any time for any reason. Should a participant decide to withdraw from the study, the study measurements made prior to withdrawal may be included in the scientific analysis and publication of the study results. Upon completion of the study and data analysis, which may take up to

four years, any remaining blood samples will be discarded. To withdraw from the study, a participant can contact the study PI ([name]).

RECRUITMENT AND RETENTION

This team has successfully recruited for KHCO₃ intervention trials. In our dose-finding KHCO₃ trial, we recruited and enrolled 244 older adults over a 31-month period,²⁵ completing enrollment 7 months ahead of schedule. Recruitment will be done in ways that have been successful for us in the past, including:

Local recruitment methods:

- 1) We will identify appropriate potential candidates (i.e., those who meet our age criteria and whose participation in prior studies would not make them ineligible) in the HNRCA Recruitment database, and send them a recruitment letter and an email. We will also send a modified recruitment letter and email to potential candidates who received a recruitment letter for this study >1 year ago, to reassess their interest. Interested individuals may call or reply via email for more information about the study and their potential eligibility (opt in). A follow up call or email will be made to those people who do not reply. A voicemail will be left for those who do not answer the telephone.

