The investigator's central hypothesis is that higher protein intake and a neutralizing alkaline salt will improve muscle performance and mass, compared to their respective placebos, in older men and postmenopausal women. To test the hypothesis, the investigators conducted a randomized, double-blind, placebo-controlled, 2x2 factorial study in underactive men and women age 65 and older on baseline lower protein diets. Participants were assigned to one of four groups: either a whey protein (WP) supplement (to raise protein intake to 1.5 g/kg/d) with or without potassium bicarbonate (KHCO_3) 81 mmol/d or an isocaloric placebo supplement with or without KHCO_3 81 mmol/d for 24 wks.

b. *Objectives*

Primary aim: Evaluate the effects of whey protein (WP) and of KHCO_3 on lower extremity muscle power at 24 weeks. This factorial ("at-the-margins") analysis will evaluate the effects of WP vs. placebo-WP and of KHCO_3 vs. placebo- KHCO_3 by using an ANCOVA approach comparing the primary outcome between groups with adjustment for baseline lower extremity muscle power, sex, age and factorial design.

Secondary aims: Evaluate the effects of WP and of KHCO_3 in terms of lower extremity muscle power at 12 weeks, knee extension torque at 12 and 24 weeks, physical performance at 24 weeks, lean mass at 24 weeks, handgrip strength at 24 weeks, physical performance battery at 24 weeks, and 24-hr urinary nitrogen excretion (UNi).

4. Study Methods

a. *Trial design*

This is a single-center, individually randomized, 2x2 factorial, placebo-controlled trial.

Participants were randomized in a 1:1:1:1 fashion to:

- whey protein isolate + KHCO_3
- whey protein isolate + microcrystalline cellulose
- maltodextrin powder + KHCO_3
- maltodextrin powder + microcrystalline cellulose

b. *Randomization*

Randomization was stratified by sex, by using block randomization (randomly permuted block sizes of 4 or 8). The random allocation sequence was computer-generated by a biostatistician. The randomization sequence was incorporated into the online Electronic Data Capture system. Central randomization via the online EDC system maintained allocation concealment.

c. Sample size

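### SAP 7d credits the primary analysis with using all available follow-up data by REML under MAR, but the primary model is a week-24-only ANCOVA that ignores week-12 power

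*SAP*

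**What the plan says.** SAP 7d (Missing data) describes the primary analyses thus: "we will analyze all available follow-up outcome data using restricted maximum likelihood estimation, under the assumption that data are missing at random". A sentence earlier it deals with reporting: "The number of missing primary outcome data points at each time point, by intervention arm, will be reported" in the CONSORT diagram.

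The primary model is set out elsewhere. SAP 3b (Objectives) describes "using an ANCOVA approach comparing the primary outcome between groups", adjusted for baseline power, sex, age and the factorial design. SAP 7b (Analysis methods, Primary Outcome) says the primary analysis is performed on the ITT sample, "based on an ANCOVA comparing 24-week leg power with fixed effects for intervention groups", adjusted for baseline power, age, sex and the other intervention. It adds: "Type III sum-of-squares will be used to test significance of each intervention". SAP 7a fixes the outcome at 24 weeks, and Table 2 reports an LS-mean difference for each margin.

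In 7b, REML is specified only for a longitudinal model fitted in addition to the ANCOVA. That model has weeks 12 and 24 as outcome rows, and baseline (also by time) and sex as covariates; age is not listed. On what it reports, the SAP says: "The corresponding treatment effect measure is the between-group difference in the slopes of the mean responses". Its p value comes from the group-by-time term.

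On who is analysed, SAP 5c says: "The full analysis set will include all randomized subjects". The protocol (Withdrawal of subjects) says that "the study measurements made prior to withdrawal may be included in the scientific analysis and publication of the study results". Multiple imputation is a sensitivity analysis in 7d.

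**The concern.** An ANCOVA with one outcome value per person has no place for a week-12 measurement. Someone with baseline and week-12 power but no week-24 power contributes nothing to it, and fitting it by REML changes nothing. So 7d gives the primary analysis a property that its model lacks.

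Two things are at stake. First, a report that follows 7d would describe an analysis of participants with observed week-24 values as one that uses all follow-up data under MAR. Second, the protection differs. A joint model of weeks 12 and 24 allows drop-out to depend on week-12 power, which the trial measures (Protocol, Muscle Measures and Physical Activity). The week-24 ANCOVA does not.

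**Working it through.** **1. The texts side by side.**

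| | SAP 7d, for the primary analyses | Primary model, SAP 3b and 7b | Longitudinal model, SAP 7b |
|---|---|---|---|
| Outcome rows | all available follow-up | week 24 only | weeks 12 and 24 |
| Estimation | REML | linear model, Type III sums of squares | REML |
| Age as covariate | not stated | yes | no |
| Reported effect | not stated | week-24 LS-mean difference | slope difference (group by time) |

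The longitudinal model fits the 7d description, but it is not the primary analysis. Because time is categorical, the week-24 difference can be computed from that fit as the group effect plus the week-24 group-by-time term. The SAP does not commit to reporting it.

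**2. The plan's own figure, as background.** Nothing here disputes it. Power is approximately Φ(δ/(SD·√(2/n)) − 1.96), with n = 60 per margin (SAP 4c).
- KHCO₃: 6/(12 × 0.1826) − 1.96 = 0.78, giving 78.2% (stated 80%).
- Whey: 8/(15 × 0.1826) − 1.96 = 0.96, giving 83.2% (stated 80%).

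**3. Inputs for size.** The target of 120 completers is from the protocol (Human Subjects Involvement, Characteristics and Design). Drop-out rates, correlations and dependence slopes are assumptions. Units are residual SDs of week-24 power, because the SAP's 12% is an SD of percent change. The SE of a margin difference is √(2/60) = 0.183 SD.

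**4. People affected.** Those missing week 24 number 120/(1 − q) − 120, which is 13 at q = 10% and 30 at q = 20%. If half to all of them have week-12 power, the ANCOVA leaves out 7–13 or 15–30 people with follow-up data.

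**5. Precision under random drop-out.** With r the correlation between visits and f the share of those missing week 24 who have week-12 data, using week 12 reduces the variance by r²qf/(1 − q + qf).

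| f | q | r = 0.5 | r = 0.7 |
|---|---|---|---|
| 1 | 10% | 2.5% | 4.9% |
| 1 | 20% | 5.0% | 9.8% |
| 0.5 | 10% | 1.3% | 2.6% |
| 0.5 | 20% | 2.8% | 5.4% |

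If drop-out depends strongly on week-12 power, simulation puts the gain at about 1–4%.

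**6. Bias of the week-24-only estimate.** Let z be the week-12 residual in SDs and let drop-out probability be expit(a − bz), with a set to give each arm's rate. The bias is r × (mean z among completers in one arm − mean z in the other). The ranges cover b = 0.5 to 1.0 and r = 0.5 to 0.7.

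Example, 15% vs 5%, b = 1, r = 0.7: mean z is 0.133 and 0.047, so the bias is 0.7 × 0.0855 = 0.060 SD, and 0.060/0.183 = 0.33 SE.

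| Drop-out pattern | Bias (SD) | Bias (SE) |
|---|---|---|
| 10% vs 5% | 0.012–0.031 | 0.07–0.17 |
| 15% vs 5% | 0.024–0.060 | 0.13–0.33 |
| 10% vs 5%, half leaving before week 12 at random | 0.007–0.017 | 0.04–0.09 |
| 15% vs 5%, half leaving before week 12 at random | 0.014–0.035 | 0.07–0.19 |
| Equal rates, equal dependence | 0 | 0 |
| Equal 10%, dependence in one arm only (b = 1) | 0.045–0.064 | 0.25–0.35 |
| Equal 20%, dependence in one arm only (b = 1) | 0.087–0.121 | 0.47–0.66 |

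In a simulation of 3,000 trials with 66 per margin, 15% vs 5% and b = 1 gave ANCOVA bias of 0.044 SD (r = 0.5) and 0.055 SD (r = 0.7). The two-visit likelihood estimate was biased by at most 0.005 SD over all cells.

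**7. Effect on the test.** With a bias of d SE, two-sided type I error is 1 − Φ(1.96 − d) + Φ(−1.96 − d). For d = 0.07 to 0.33 this is 5.1% to 6.3%. For d = 0.66 it is about 10%.

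**The case against.** The strongest reply is that the sections are compatible. In a one-outcome linear model, REML and least squares give the same fixed effects and standard errors. All available data can then mean every observed week-24 value, with MAR conditional on the covariates. This reading is possible. The count of missing values by time point suggests more than one visit, but it is a reporting sentence and does not settle the matter. Nor do the definition of the full analysis set or the protocol's withdrawal clause. Even so, 7d does not say that the analysis is limited to observed week-24 values, and it does not state the narrower missingness condition.

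It is also fair that much is covered elsewhere. The imputation treats repeated measurements as distinct variables in wide format, so it can use week 12; the weaker wording, under which outcome data are only to be considered, concerns auxiliary variables. Attrition comparisons are planned, week-12 power is a secondary outcome in its own right, the trial is double-blind, and participants who stop treatment are generally encouraged to stay and complete measurements (Protocol, Protection of study blinding). All of this stands, and it keeps the issue modest.

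A reader might infer that the primary analysis or its target is ambiguous and that a repeated-measures model should replace it. The documents do not support that: SAP 3b, 7a, 7b and Table 2 agree on a week-24 LS-mean difference from an ANCOVA. A reader might also infer that the trial loses power. That does not follow, because the target is 120 completers.

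**Conclusion.** The mismatch is real and should be corrected. SAP 7d claims a missing-data property that the primary model in 3b and 7b does not have, or, on the milder reading, leaves out the condition on which that model is valid: week-24 missingness depending on arm, baseline power, age and sex alone.

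The likely effect is modest. Differential drop-out that depends on week-12 power gives about 0.07–0.33 SE of bias, and less if some leave before week 12. Equal drop-out with equal dependence gives none. Only dependence in one arm alone, an extreme case, goes beyond that range, up to 0.66 SE. Week-12 data would lower the variance by about 1–10%. Every one of these figures rests on assumed rates, slopes and correlations, so they show scale and do not forecast this trial.

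It would be too strong to say that the plan has no way of estimating the week-24 difference from all the data. The two-visit fit contains that contrast and the imputation can use week 12. What is missing is the commitment to report the contrast, with age in the model, and to use week-12 power in the imputation.

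**What to change.** Before outcomes are examined by group:

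1. Keep the week-24 ANCOVA as the primary analysis.
2. Reword 7d to say that it uses participants with an observed week-24 value, and that it is valid if missingness depends only on arm, baseline power, age and sex.
3. Add age to the planned two-visit REML model. Report its week-24 LS-mean difference for each intervention, adjusted for the other, beside the slope contrast, and name it as the all-available-data analysis under MAR.
4. State in 7d that week-12 power will be in the imputation model, in place of saying that outcome data will be considered.

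The cost is two reworded sentences, one covariate and one extra reported contrast, with no new data or visits. Replacing the primary model is not recommended: it is stated consistently in 3b, 7b and Table 2.
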